- **Exposed during pregnancy by trimesters** – *in utero* exposed to anifrolumab will be determined for each pregnancy trimester (dichotomous variables) and combined into a pattern of exposure by trimester (Table 6). The exposure by trimester will be defined as:
 - in each trimester, offspring whose mother had at least one prescription/dispensations/administration of anifrolumab leading to an exposure period overlapping with a specific trimester(s), will be classified as exposed (yes/no) (Table 6);
 - offspring whose mother had no anifrolumab prescription/dispensations/administration in the 16 weeks (anifrolumab window of clearance) prior to LMP2 or during all pregnancy, with the assumption of continuing treatment with SOC, will be classified as non-exposed (yes/no) (Table 6).

Table 6: Maternal exposure status by trimester, offspring *in utero* exposed to anifrolumab (polytherapy) vs offspring *in utero* exposed to SLE SOC

Exposed group				Comparator group		
1 st trimester	2 nd trimester	3 rd trimester		1 st trimester	2 nd trimester	3 rd trimester
anifrolumab (+ SOC)	SOC ¹	SOC ¹	VS	SOC	SOC ¹	SOC ¹
anifrolumab (+ SOC)	anifrolumab (+ SOC)	SOC ¹	VS	SOC	SOC	SOC ¹
anifrolumab (+ SOC)	anifrolumab (+ SOC)	anifrolumab (+ SOC)	VS	SOC	SOC	SOC
SOC	anifrolumab (+ SOC)	anifrolumab (+ SOC)	VS	SOC	SOC	SOC
SOC	SOC	anifrolumab (+ SOC)	VS	SOC	SOC	SOC

Abbreviations used in the table: SOC, Standard of care; VS, Versus

¹ SOC might not be applicable if pregnancy ends early

Definition of exposure period

Women exposed to anifrolumab during pregnancy are included in the exposed groups regardless of the exposure status before pregnancy. The maximum exposure period is from LMP2 to delivery/birth. The maternal exposure period during pregnancy is not considered to be fixed. This is because pregnancy duration is not exactly the same for all pregnancies (full-term birth is considered between 37 to 42 weeks of gestation). Also, exposure period can end earlier with a censoring event (e.g., elective termination of pregnancy).

The definition of exposure period relies on available information on the date of prescription/dispensation/administration, the expected supply (i.e., package size, the number of packages prescribed/dispensed), and the estimated window of drug clearance (for anifrolumab, the time for concentration to fall below the LLOQ for 95% of patients is 16 weeks from last administration). The exposure period starts on the date when the drug was administered or

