prescribed/dispensed (if information on the date of dispensation is not available, the start of the exposure period will be defined based on the date when the prescription was issued). The end date of the exposure period is calculated by adding the estimated window of clearance and expected supply to the prescriptions/dispensations/administrations date (Figure 6).

[figure not shown]

Figure 6: Anifrolumab exposure period

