To describe and estimate the risk of select pregnancy loss outcomes (composite of spontaneous abortion and stillbirth) in pregnancies occurring in women with moderate/severe SLE who were exposed or unexposed to anifrolumab in specific pregnancy trimesters (study objective 13), the pregnancy trimester specific exposure groups where the exposure to the study or comparator treatment is during a specific pregnancy trimester (trimester 1 only; trimester 1&2 only; trimester 2&3 only; trimester 3 only; all trimester 1&2&3) will be generated from the *pregnancy* cohort (as defined in Section 9.2.2). The analysis for the pregnancy trimester specific exposure groups will be performed separately by comparing each exposed group and its comparator group as shown in Table 6 in Section 9.3.1. This requires that the PS adjustment is done separately for 5 exposure group comparisons i.e., 5 different PS models will be fitted on each of the exposure group comparisons separately. Also, the crude and adjusted cumulative incidence will be calculated separately for each of the 5 exposure group comparisons (as shown in Table 6 in Section 9.3.1) to estimate the risk of the select pregnancy loss outcomes in pregnancies occurring in women with moderate/severe SLE with pregnancy trimester specific exposure to the anifrolumab. The crude cumulative incidence (i.e., risk) will be calculated as the total number of select pregnancy loss outcomes (composite of spontaneous abortion and stillbirth) divided by the total number of pregnancies in pregnancy trimester specific study cohorts. The adjusted cumulative incidence (i.e., risk) will be estimated following PS adjustment.

Objective 14

To estimate the relative risk of select pregnancy loss outcomes (composite of spontaneous abortion and stillbirth) in pregnancies occurring in women with moderate/severe SLE and who were exposed anifrolumab in specific pregnancy trimester (study objective 14), the crude and adjusted RRs (with corresponding 95% CI) will be estimated separately for each specific pregnancy trimester exposure groups as defined in Section 9.7.1. The crude RR will be estimated separately for each pregnancy trimester specific exposure groups using a regression model as specified in Section 9.7.1. The adjusted RR will be estimated using the same regression model following an appropriate PS adjustment method as described in Section 9.7.1.

Objective 15

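### Objectives 13-14 group pregnancies by a final trimester pattern that pregnancy loss itself truncates, so the trimester-1-only group collects every exposed first-trimester loss

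*Protocol*

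**What the plan says.** Section 9.3.1 scores each trimester separately. A dose "leading to an exposure period overlapping with a specific trimester(s), will be classified as exposed (yes/no"), and the three scores are combined into a pattern. On length of exposure, "The end date of the exposure period is calculated by adding the estimated window of clearance and expected supply" to the dose date; for anifrolumab, "the time for concentration to fall below the LLOQ for 95% of patients is 16 weeks from last administration". Pregnancy length then limits this, because the "exposure period can end earlier with a censoring event (e.g., elective termination of pregnancy").

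Table 6 and Section 9.7.4 list five patterns: "trimester 1 only; trimester 1&2 only; trimester 2&3 only; trimester 3 only; all trimester 1&2&3". Footnote 1 of Table 6, "SOC might not be applicable if pregnancy ends early", is attached to the later-trimester SOC cells of the trimester-1-only and trimester-1&2 rows, so early-ending pregnancies stay in those rows. The exposed arms of the other three rows carry no such allowance.

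Under Objective 13 the crude risk is the number of losses "divided by the total number of pregnancies in pregnancy trimester specific study cohorts", and "5 different PS models will be fitted on each of the exposure group comparisons separately". Objective 14 takes risk ratios from the same groups. Its comparator is women on SOC in the same trimesters, while Section 9.3.1 assumes that SOC continues throughout pregnancy.

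**The concern.** The final pattern is known only when the pregnancy ends, and the outcome is one of the things that ends it. Two women with the same dosing are put in different groups because one lost the pregnancy in trimester 1 and the other did not. A denominator of everyone in the final pattern then conditions on survival.

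Section 9.3.1 presents this analysis as a search for critical exposure windows that could guide protection of the foetus, and Section 7.4 cites embryo-foetal loss as the nonclinical signal. A first-trimester excess produced by the grouping rule would bear on exactly that question. Propensity scores cannot repair it: Section 9.7.1 uses covariates measured at or before conception or the start of exposure, and the error comes from survival after that.

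**Working it through.** **Patterns.** Three yes/no scores give 2³ − 1 = 7 non-empty patterns. The protocol's count of five comparisons is reproduced by its list; trimester 2 only and trimesters 1&3 are absent. The patterns a pregnancy can reach depend on when it ends:

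- Ends in trimester 1: trimester 1 only.
- Ends in trimester 2: trimester 1 only, trimesters 1&2, or trimester 2 only (no group).
- Ends in trimester 3: any of the seven.

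Four of the five groups therefore contain no first-trimester loss by construction. A woman who starts in trimester 2 and loses the pregnancy in trimester 2 has no group; if she loses it in trimester 3 she is in trimesters 2&3.

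**Carry-over.** The protocol gives no week limits for trimesters, so assume trimester 1 ends at gestational week 12-14. LMP2 is week 2. A continuing pregnancy is trimester 1 only if its last dose was before week 12 − 16 = −4 to 14 − 16 = −2, that is, at least about 6 to 4 weeks before LMP2. A dose at LMP2 carries to week 2 + 16 = 18, which is in trimester 2. So a woman dosed at or after LMP2 is trimester 1 only just when her pregnancy ended in trimester 1.

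**Size under no effect, comparator read as SOC pregnancies of any length.** Let the loss risk be 0.20 in both groups (Section 9.5.1.1), t the part lost in trimester 1, and s the share of continuing first-trimester-exposed pregnancies that stay trimester 1 only. Then

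risk in trimester 1 only = [t + s(0.20 − t)] / [t + s(1 − t)], and RR = risk / 0.20.

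The protocol gives neither t nor s. Section 9.9 says only that most outcomes ending a pregnancy are expected in the first trimester. Illustration A takes the last dose as uniform from week −14 (16 weeks before LMP2) to week 8, with trimester 1 ending at week 14. Then s = 12/22 = 0.545. With 50%, 70% and 90% of losses in trimester 1:

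- t = 0.10: 0.1545/0.5909 = 0.262, RR 1.31
- t = 0.14: 0.1727/0.6091 = 0.284, RR 1.42
- t = 0.18: 0.1909/0.6273 = 0.304, RR 1.52

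A simulation of 2,000,000 pregnancies per scenario gave 0.262, 0.283 and 0.304.

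Illustration B varies s, with t = 0.12 and 0.16:

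- s = 0.50: 0.16/0.56 and 0.18/0.58, RR 1.43 and 1.55
- s = 0.20: 0.136/0.296 and 0.168/0.328, RR 2.30 and 2.56
- s = 0.10: 0.128/0.208 and 0.164/0.244, RR 3.08 and 3.36

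**Later patterns, Illustration A.** The risk in trimesters 1&2 is (0.20 − t)/(1 − t): 0.10/0.90 = 11.1%, 0.06/0.86 = 7.0% and 0.02/0.82 = 2.4%. The simulation, with 10% starting in trimester 2 and 10% in trimester 3, put trimesters 2&3 at about 1-4% and trimester 3 only at about 0.6-2%. The true whole-pregnancy risk is 20% throughout.

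**Losses with no group.** Take trimester 2 starts and losses as uniform over the trimester, so half of the trimester 2 losses follow the start. With losses split 50/35/15, 70/20/10 and 90/5/5 across trimesters, the share of losses among trimester 2 starters that has no group is 17.5/32.5 = 54%, 10/20 = 50% and 2.5/7.5 = 33%.

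**Comparator read literally as SOC in trimester 1 only.** Because SOC is assumed to continue, such a comparator is mostly pregnancies that ended in trimester 1. Its loss risk is inflated far above 20%, and the ratio could even reverse.

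**The case against.** The best defence is that the analysis is exploratory, run per data source, not meta-analysed and already limited by small-cell rules. Section 9.9 also concedes immortal time and a link between pregnancy length and exposure, and expects few women to start anifrolumab in trimester 2 or 3. All of this stands and limits the impact. But the Section 9.9 concession concerns exposed versus unexposed in general. Its reassurance, that most losses occur in trimester 1, works the other way here: early losses are what fill the trimester-1-only group.

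For the later rows, Table 6 asks for SOC in the same trimesters, so survival is partly mirrored and the ratios are less distorted than the absolute risks. That also stands.

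A reader might infer more than the documents support:

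- That the comparator simply is all SOC pregnancies. This is one reading; Objectives 13-14 also say the same trimesters.
- That the analysis would show a large harm for trimester 1 and none for later patterns. Ratios of 2.3-3.4 need s of 20% or less, for which the protocol gives no basis. The later ratios depend on the comparator reading; trimester 2 losses can collect in trimesters 1&2 in the same way.
- That every loss after a trimester 2 start is dropped. Those in trimester 3 are counted.

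**Conclusion.** The point holds as a structural fault in Objectives 13-14. The overlap rule, truncation by the end of pregnancy, the 16-week carry-over and the denominator are all stated in the protocol, so this is not a detail left to the SAP. That all exposed first-trimester losses fall in one group follows from the definitions alone. That continuing pregnancies dosed at or after LMP2 are shut out of that group also needs trimester 1 to end at about week 12-14.

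If the comparator is SOC pregnancies of any length, the trimester-1-only ratio is biased upward under no effect: about 1.3-1.6 for illustration, and higher if few continuing pregnancies stay in the group. Those figures rest on assumed dose timing, loss timing and shares, and ignore elective terminations. Under the literal reading the ratio is not interpretable. Absolute risks in the later patterns are artificially low. Primary Objectives 3-4 do not use these patterns and are not affected, so this should be corrected but does not threaten the main result.

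**What to change.** Replace the final-pattern comparison in Section 9.7.4 and Table 6 with one of two approaches:

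- time-varying anifrolumab exposure from LMP2; or
- trimester-specific risk sets: pregnancies still ongoing at the start of each trimester in both groups, exposure within that trimester updated over time, losses counted from that point, and at-risk denominators.

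Apply the same rule to the SOC comparator and state it once, which removes the two readings. Trimester 2 starters who lose the pregnancy in trimester 2 are then counted.

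Two nearby remedies should be avoided. A final-pattern trimester-2-only group would recreate the fault: a dose at week 12-14 or later carries to week 28-30 or later, so if trimester 2 ends by week 26-28 the group would hold almost only pregnancies that ended in trimester 2. A landmark that uses exposure only up to the start of a trimester would miss exposure during it.

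The change is to analysis wording and uses the same data. The cost is somewhat more analysis work and sparse strata in the later trimesters.

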9.7.5 Sensitivity analyses

Re-definition of the pre-conception exposure window for patients who receive prescriptions/dispensations/administrations of anifrolumab in the period prior to LMP2

The rationale for this sensitivity analysis is to explore the robustness of the exposure definition to changes in the pre-conception exposure ascertainment time-window for patients who receive anifrolumab prior to LMP2. While it is reasonable to assume that an unborn child could be exposed to anifrolumab if the mother has had a dose of anifrolumab in the 16 weeks prior to conception (LMP2), based on the population pharmacokinetics of anifrolumab, where time for concentration to fall below the LLOQ for 95% of patients is 16 weeks (2), it is also plausible that the serum concentrations may be so low (or even absent) at the time of pregnancy. Therefore, using the exposure ascertainment period of 16 weeks prior to LMP2 could result in exposure misclassification. There is a possibility that this misclassification could affect the measure of association between the exposure of interest and the outcomes of interest.

Therefore, to reduce the potential risk of exposure misclassification, the following alternative pre-conception time-windows for anifrolumab exposure will be considered:

- a) up to 8 weeks prior to LMP2 until end of the first trimester for the outcome of MCM, and up to 8 weeks prior to LMP2 until end of pregnancy for select pregnancy loss outcomes (composite of spontaneous abortion and stillbirth).
- b) from LMP2 until end of the first trimester for the outcome of MCM, and from LMP2 until end of pregnancy for select pregnancy loss outcomes (composite of spontaneous abortion and stillbirth).

Re-definition of the pre- and post-conception exposure window for the exclusion of SLE SOC and non-SLE SOC drugs with a confirmed teratogenic effect

After 4- to 5-half-lives, the plasma concentrations of a given drug is below a clinically relevant concentration and is considered eliminated. However, after 2- to 3-half-lives, the plasma concentration can be considered (very) low (56). Further, the etiologically relevant window, where the foetus is most susceptible to teratogens, is the first trimester of pregnancy for the MCM outcome (98). The rationale for this sensitivity analysis is to explore alternative pre- and post-conception exposure windows when estimating the relative risk and adjusted relative risk of MCM and select pregnancy loss outcomes (composite of spontaneous abortion and stillbirth):

- a) Pregnancies exposed to confirmed teratogenic drugs up to 1-half-life prior to LMP2 until end of the first trimester for the outcome of MCM, and up to 1-half-life prior to LMP2 until end of pregnancy for select pregnancy loss outcomes (composite of spontaneous abortion and stillbirth), in both the exposed and unexposed groups, will be excluded.
- b) Pregnancies exposed to confirmed teratogenic drugs from LMP2 until end of the first trimester for the outcome of MCM, and from LMP2 until end of pregnancy for select pregnancy loss outcomes (composite of spontaneous abortion and stillbirth), in both the exposed and unexposed groups, will be excluded.

Inclusion of offspring in utero exposed to SLE SOC and non-SLE SOC drugs regardless of the teratogenic effect

For the main analysis, pregnancies exposed to confirmed teratogenic drugs are excluded. However, in real world settings, patients may be exposed to other teratogens in pregnancy. Therefore, this sensitivity analysis will provide a “real-world” estimate of risk in a setting which is reflective of clinical practice.

To estimate the relative risk of MCM in live and non-live offspring from women exposed to anifrolumab during the first trimester of pregnancy compared to women with SLE exposed to SLE SOC and unexposed to anifrolumab during the first trimester of pregnancy.

To estimate the relative risk of select pregnancy loss outcomes (composite of spontaneous abortion and stillbirth) from women exposed to anifrolumab anytime during pregnancy compared to women with SLE exposed to SLE SOC and unexposed to anifrolumab anytime during pregnancy.

For both primary outcomes, in the calculation of the adjusted relative risk, a PS adjustment will be performed to control for confounding including the use of confirmed teratogenic drugs.

Exposure to anifrolumab monotherapy or polytherapy added to SLE SOC

The rationale for this sensitivity analysis is two-fold. While anifrolumab is indicated as an add-on medication (i.e., polytherapy) for moderate/severe SLE, it is possible that not all SLE medications being taken by a patient are captured in the database. Therefore, patients who seem to be on monotherapy may in fact be on polytherapy.

The relative risk of MCM in live and non-live offspring from women exposed to anifrolumab (monotherapy or polytherapy added to SLE SOC, excluding SLE SOC and non-SLE SOC drugs with a confirmed teratogenic effect) during the first trimester of pregnancy, compared to women with SLE exposed to SLE SOC (excluding SLE SOC and non-SLE SOC drugs with a confirmed

teratogenic effect) and unexposed to anifrolumab during the first trimester of pregnancy, will be estimated using the same approach as for study objective 2 (primary objective) as described in Section 9.7.2.

The relative risk of select pregnancy loss outcomes (a composite of spontaneous abortion and stillbirth) from women exposed to anifrolumab (monotherapy or polytherapy added to SLE SOC, excluding SLE SOC and non-SLE SOC with a confirmed teratogenic effect) anytime during pregnancy, compared to women with SLE exposed to SLE SOC (excluding SLE SOC and non-SLE SOC with a confirmed teratogenic effect) and unexposed to anifrolumab anytime during pregnancy, will be estimated using the same approach as for study objective 4 (primary objective) as described in Section 9.7.2.

Inclusion of exposed and unexposed pregnancies, irrespective of SLE severity, in the 12 months prior to conception

The rationale for this sensitivity analysis is that treatment with anifrolumab may reduce disease severity and the disease severity algorithm may misclassify patients. Therefore, this sensitivity analysis aims to minimise bias that may be arising from these phenomena.

The relative risk of MCM in live and non-live offspring from women with SLE, irrespective of SLE severity, in the 12 months prior to LMP2 exposed to anifrolumab (excluding SLE SOC and non-SLE SOC drugs with a confirmed teratogenic effect) during the first trimester of pregnancy, compared to women with SLE, irrespective of SLE severity, in the 12 months prior to LMP2 exposed to SLE SOC (excluding SLE SOC and non-SLE SOC drugs with a confirmed teratogenic effect) and unexposed to anifrolumab during the first trimester of pregnancy, will be estimated using the same approach as for study objective 2 (primary objective) as described in Section 9.7.2.

The relative risk of select pregnancy loss outcomes (a composite of spontaneous abortion and stillbirth) from women with SLE, irrespective of SLE severity in the 12 months prior to LMP2, exposed to anifrolumab (excluding SLE SOC and non-SLE SOC drugs with a confirmed teratogenic effect) anytime during pregnancy, compared to women with SLE, irrespective of SLE severity in the 12 months prior to LMP2, exposed to SLE SOC (excluding SLE SOC and non-SLE SOC drugs with a confirmed teratogenic effect) and unexposed to anifrolumab anytime during pregnancy, will be estimated using the same approach as for study objective 4 (primary objective) as described in Section 9.7.2.

Exposure re-definition

Although it is expected that patients will generally take medications as prescribed, it is possible that patients may not fully comply with prescribed medications. Therefore, to reduce the risk of exposure misclassification, exposure to anifrolumab will be defined as having at least two claims for filled prescriptions/dispensations/administrations during the etiologically relevant exposure time window. This sensitivity analysis will be conducted for the all the primary objectives following methods described in Section 9.7.1 if sample size allows.

Unmeasured confounding for primary study outcomes

The rationale of this sensitivity analysis is to examine the robustness of the primary study outcome (MCM and select pregnancy loss outcomes) analysis results to unmeasured confounding. Quantitative bias analysis methods will be used for studying the effect of unmeasured confounding on the study results (68). The quantitative bias analysis methods will be selected depending on what is known about the potential unmeasured confounder and its relationship between the exposure and the primary study outcomes (26). If the effect of a specific confounder and its relationship between the exposure and the primary study outcomes is well understood, a simple equation may be used for quantifying the confounder's relationship to exposure and primary study outcomes. This method allows to estimate the primary study outcome analysis results after adjusting for the specific unmeasured confounder (26). This approach could be considered in cases where a specific confounder is measured in some but not all data sources (listed as a limitation in Section 9.9). In case nothing is known about a potential unmeasured confounder, methods such as the E-value approach may be considered (26). The E-value approach aims to assess how strongly an unmeasured confounder would have to be related to anifrolumab exposure and primary study outcomes to explain away (i.e., nullify) the observed association of anifrolumab exposure with the primary study outcomes (112). Further details on the methods will be provided in the SAP.

Account for actual use of SLE SOC during pregnancy

The rationale for this sensitivity analysis is to account for actual use of SLE SOC during pregnancy in estimating the risk and relative risk of primary study outcomes. For the main analysis, the SLE SOC is assumed to be continued throughout pregnancy. In this sensitivity analysis, an exact matching criterion will be added to the PS matching step of the cohort building. For a given anifrolumab exposed pregnancy, the set of potential matches will be restricted to pregnancies unexposed to anifrolumab and exposed to SLE SOC during the same trimester(s) as the exposed pregnancy was exposed to anifrolumab. For example, if a given exposed pregnancy is exposed to anifrolumab during the second and third trimester, potential matches will be restricted to unexposed pregnancies with SLE SOC exposure during the second and third trimester. After matching, the sensitivity analysis will be conducted as described for Objectives 1-4 (see Section 9.7.2).

Exposure to anifrolumab and risk of MCM using the MACDP classification system for congenital malformations

This study comprises both European and American data sources; therefore, the MACDP USA-based classification system, in addition to the EUROCAT, for MCM will be used.

The MACDP classification system categorises and defines congenital malformations differently from EUROCAT, and the results obtained from each classification system may differ. Since it is essential to consider the potential impact of different categorisations and definitions of congenital malformations on the results, a sensitivity analysis will be performed using the MACDP classification system. The rationale of this sensitivity analysis is to examine the robustness and

reliability of the association between exposure to anifrolumab and the risk of MCM using the MACDP classification (59).

